8.2 Describe any primary or secondary safety endpoints

Before the procedure, a medication line will be inserted into a vein in the subject's arm. An oxygen monitor and blood pressure cuff will also be placed. Subjects will be positioned on their back for this procedure. Their neck will be swabbed with disinfectant to clean the skin, and sterile equipment and technique will be used for the entire of the procedure.

After the study procedure is completed, subjects will stay in the office for half an hour for observation. Blood pressure will be checked. All subjects will have a peripheral intravenous catheter (a plastic tube to take blood and give medicines without having to stick the vein multiple times) placed in their arm prior to the procedure, and temperature monitoring of the arm and hand, evaluation for temporary drooping of the right eyelid, redness in the eye, congestion in the nose, and sweating on the right side of the face will be performed. These confirmatory signs of proper SGB placement will not be recorded as AEs.

The study team will meet and review all adverse events after five subjects have been randomized and received the SGB procedure or sham. Per NU IRB protocol, all UPIRSO's or PRNCs will be reported as soon as the PI becomes aware of it. As the PI is the injectionist, the likelihood of missing a UPIRSO is highly unlikely. If no SAEs/UPIRSO's are observed, the team will meet again after 10 subjects have been randomized. No UPIRSOs or SAEs have occurred in previous studies.

9.0 Procedures Involved

9.1 Describe and explain the study design.

Title: SGB CA Study

We aim to conduct a randomized, single-site, sham-control clinical trial of SGB on VMS in 36 women with breast cancer on anti-estrogen therapy (18 per group). We will need to screen and enroll approximately 50 women to randomize 36 women. Some women may not qualify due to insufficient number of hot flashes or there may be some withdrawals. The primary entry criterion will be 28 or more moderate to very severe hot flashes per week. VMS will be measured by self-report on a written daily dairy over a 6-month period. Secondary outcomes include changes in mood, sleep, quality of life, memory performance with neurocognitive testing, and objective hot flashes measured by ambulatory monitoring (skin-conductance temperature monitoring) for 24 hours at baseline, three months and six months.

Randomization and Masking Procedures A computer-generated 1:1 block randomization scheme will be used to assign participants to receive either a SGB with bupivacaine or a sham injection with saline. Randomization will be performed by the injectionist immediately before the injection procedure by opening an opaque envelope to reveal the participant number and group assignment printed on an index card. Randomization assignment will be kept under lock and key. Participants and all other study personnel, including those who will perform follow-up evaluations, will be blinded to group assignment. The injectionist will not have access to the written VMS diaries until the conclusion of the study.

9.2 Provide a description of all research procedures being performed and when they are performed, including procedures being performed to monitor subjects for safety or minimize risks.

Screening Visit 1

Recording of Hot Flashes

After the participant has reviewed and signed the consent form, they will be interviewed to determine if they are a candidate for the study. We will ask them to provide information about themselves and their medical history. A member of the study team will administer the Depression Anxiety and Stress Scale (DASS) to ensure that participants are not suffering from extreme anxiety or depression. If they are found to have any of these conditions and meet the exclusion criterion, they will not qualify for our study and will be referred to a mental health provider.

Before having the SGB procedure participants will be asked to maintain a daily paper diary of their hot flashes, recording the number and severity using a scale that will be provided to them. They will be asked to do this a minimum of two weeks prior to the SGB procedure in order to determine if they are eligible for the study. They will also record any comments about the hot flashes they experience each day.

At the end of two weeks, a member of the study team will telephone to ask how many hot flashes they are experiencing in a week. If they qualify based on the total number of hot flashes, they will be scheduled to return to the research office for placement of the hot

Title: SGB CA Study

flash monitor, actigraph watch, questionnaire completion and cognitive testing procedures which are described separately.

The study procedure with [name] in the Department of Anesthesiology will be scheduled to occur at a separate visit.

Visit 2 (2 to 3 weeks after visit 1)

There are four types of research evaluations that they will be asked to complete: questionnaires, hot flash monitoring, actigraph watch monitoring and tests of mental abilities (cognitive testing). They will be asked to complete these four tasks at three time points: before the procedure, three months after the procedure, and six months after the procedure. Below we describe each of these types of research evaluations.

Cognitive Testing

They will be asked to complete some memory functioning tests that will assist us in the evaluation of the results of the study procedure. At each session, they will meet one-on-one with a research assistant who is trained in giving tests of different mental abilities. That assistant will instruct the participant on how to complete tasks that measure different mental abilities, such as memory, concentration, and language. Assessment of cognitive function has certain exclusion criteria. If they are found to be ineligible to participate in this portion of the study, they may still participate in the hot flash portion of the study.

Questionnaires

They will also complete questionnaires about mood and everyday functioning. They may refuse to answer any question that they don't wish to answer. If they become uncomfortable at any time and wish to stop, the tests will be stopped. These forms are:

- Depression Scale (CES-D)
- Depression Anxiety and Stress Scale (DASS)
- Mini-Mental State Exam (MMSE)
- McCoy Female Sexuality Questionnaire (MFSQ)
- Modified Pittsburgh Sleep Quality Index (PSQI)
- Functional Assessment of Cancer Therapy (FACT-B)
- Pain Intensity and Interference Scale (PEG)

Hot Flash Monitoring

A research assistant will attach a hot flash monitor to the participant after they have completed the above mentioned. The hot flash monitor will be returned 24-hours later to the office via UPS or, at their convenience, a research assistant can meet them to disconnect and collect the hot flash monitor at their doctor's office or back at the study site.

Title: SGB CA Study

The hot flash monitor we are using in this study is a small, lightweight, portable recorder that measures how many hot flashes you have each day. The monitor includes some wires and adhesive pads. The adhesive pads are attached to the skin on the chest just below the collarbones. Inside each adhesive pad is a small device that measures hot flashes. Wires send signals from the device to the monitor. Occasionally, the device may malfunction if the adhesive loosens or for other unknown reasons. Should this occur, they may be asked to wear the monitor for an additional 24 hours in order to collect missing objective hot flash data. The monitor measures 1 x 4 x 6 inches and weighs 8 ounces. The monitor is carried in a bag that is worn around the waist like a fanny pack. They will be given verbal instructions and handouts describing how to use the monitor.

Actigraph Watch

The research assistant will also instruct the participant on how to wear an Actigraph. An Actigraph is worn just like a watch and monitors sleep and wake habits. It should be removed for bathing, showering or swimming. They will be given verbal instructions and handouts describing how to use the actigraph watch. They will be given a prepaid return mailing box so that they can return the hot flash monitor and the Actigraph to us via UPS. Visit 3 (4-5 weeks after visit 1)

Stellate Ganglion Injection Procedure

Participants will be interviewed to assess health status and a brief physical exam will be performed by [name]. If they are determined to be a candidate for the procedure by [name], will randomize the participant into one of two groups: one group will receive the study procedure (stellate ganglion injection with local anesthetic or numbing medication) and the other will receive a sham procedure involving a saline injection in the superficial tissues of the right side of the neck in the region just below the skin layer.

Assignment to groups will be done by randomization similar to flipping a coin. They will have a 50% chance of going into either of the two groups. The study will be single blinded. Participants will not know which group they are in and only [name] will know whether they have received the stellate ganglion injection with numbing medication or the sham injection with saline. Since it is unknown how long the effects of the injection on hot flashes lasts, participants will have the option of receiving a second injection after the three month procedures if they notice an increase in the severity or frequency of their hot flashes. They will receive the same injection (bupivacaine or sham) that they got at the beginning of the study.

Before the procedure, a medication line will be inserted into a vein in the arm. An oxygen monitor and blood pressure cuff will also be placed. They will be positioned on their back for this procedure. Their neck will be swabbed with disinfectant to clean the skin, and sterile equipment and technique will be used for the entire of the procedure. With the use of a low dose x-ray machine (fluoroscopy machine) to help guide the injection, a bone in the right side of the neck (C6) will be identified and local anesthesia or numbing medicine (1% lidocaine) will be injected to the skin overlying the bone.

Title: SGB CA Study

For subjects receiving the stellate ganglion injection, a small needle will be placed through the numbed skin on the front of the right side of the neck to make contact with the tissues over the C6 (neck) bone. The correct position of this needle will be confirmed by injecting a small amount of dye that can be seen by [name] under x-ray. Then 10 cc or about 2 teaspoons of 0.5% bupivacaine (numbing medicine) will be injected and the needle will be removed.

In participants put in the sham injection group, the needle will be placed in the superficial tissues overlying the front right neck (C6 bone), just underneath the skin. 5 cc of saline fluid will be injected and the needle will be removed. This procedure will take a few minutes. After it is completed, they will stay in the office for about half an hour for observation. Their blood pressure will be checked.

As above, all subjects will have a peripheral intravenous catheter (a plastic tube to take blood and give medicines without having to stick the vein multiple times) placed in their arm prior to the procedure, and temperature monitoring of the arm and hand, evaluation for temporary drooping of the right eyelid, redness in the eye, congestion in the nose, and sweating on the right side of the face will be performed.

Visit 4 (3 months after study procedure)

They will be asked to return to the clinical site 3 months following the injection procedure. At this visit, the same procedures listed in visit 2 will be performed.

Visit 5 (6 months after study procedure)

They will be asked to return to the clinical site 6 months following the injection procedure. At this visit, the same procedures except for cognition testing listed in visit 2 will be performed.

Participants will continue to complete their hot flash diary for the duration of the study.
Their part in this study will last for approximately seven months and will involve five visits.

Additional Follow Up (6-12 months after study procedure)

Participants will be asked if they have any interest in maintaining a paper diary for an additional six months to assess longer term effects of the treatment. If they agree, a member of the research staff will call once a month for the next six months and to remind them to complete their hot flash diary and record long term effects, if any.

If they choose to continue to record their hot flashes, their participation may increase to thirteen months and they will have 6 visits.

9.3 *Describe:*

• *Procedures performed to lessen the probability or magnitude of risks.*

At the time of the injection procedure, an angiocatheter will be placed in the left hand/arm for peripheral intravenous access as a safety precaution and a temperature monitor will be placed on the right dorsal hand. Participants will be positioned supine in cervical extension. The anterior neck will be prepped with chlorhexidine and draped in

Title: SGB CA Study

the standard sterile manner. For active SGB, a right-sided SGB will be performed. Using fluoroscopic guidance, the C6 vertebra will be identified and the skin overlying the tubercle will be anesthetized using 2 mL of 1% lidocaine. Using digital pressure to laterally retract the carotid artery, a 22 g 1.5-inch needle will be placed to make contact with the anterolateral portion of the C6 vertebra and then retracted 1-2 mm and secured; contrast material (iopamidol 1-2 mL) will be injected with fluoroscopic guidance to confirm contrast dye spread in the prevertebral fascial plane and to rule out intravascular or intrathecal dye spread. 0.5% bupivacaine (10 mL) will be injected and the needle will be removed. Generally, any woman can safely have this injection unless she has an allergy to local anesthetic, contrast material, or has anatomic abnormalities of the anterior neck, all of which are rare. Drug interactions are a concern with other non-hormonal treatments for VMS, but not with SGB. The dose of local anesthetic needed to block the stellate ganglion does not cause toxic plasma levels of local anesthetic in the bloodstream and does not significantly interact with medications used for hypertension, asthma, depression, or seizures.

For sham injection, the same positioning, monitoring, sterile preparation and technique will be used with identical visual, auditory and tactile cues, except the needle will be placed in the superficial tissues overlying the C6 tubercle. With fluoroscopic guidance, contrast material (iopamidol 1-2 mL) will be injected to confirm contrast dye spread in the subcutaneous tissues, not in the prevertebral fascial plane of the stellate ganglion. Preservative-free saline (5 mL) will be injected and the needle will then be removed. Participants will be transferred to a recovery area and monitored in a reclining position for at least 20 minutes to assess potential adverse effects of the injection. Vital signs will be measured every 5 minutes during the recovery phase. Presence of a Horner's sign (miosis, ptosis, anhydrosis) will be recorded and will validate successful SGB. Pre- and post-injection temperatures of the right hand will be measured and recorded. The research team will not have access to the injectionist's procedure notes in order to maintain the blind. Miosis, ptosis, and anhydrosis will not be considered adverse events as they are confirmatory for adequate SGB placement.

- ***All drugs and devices used in the research and the purpose of their use, and their regulatory approval status.***

The study will use approved drugs (0.5% Bupivacaine, 1% Lidocaine and sterile saline) for unapproved uses (reduction in VMS). The package inserts have been uploaded into the "Supporting Documents" section of the IRB application.

- ***The source records, including medical or educational records that will be used to collect data about subjects. (Attach all surveys, scripts, and data collection forms.)***

Copies of all surveys, diaries, subject instructions, cognition testing battery and data collection forms have been uploaded under the "Supporting Documents" section of the IRB application.

9.4 *What data will be collected, including long-term follow-up.*

Baseline data for subjective VMS frequency and severity will be recorded by

Title: SGB CA Study

participants in a written diary. Additional data for depression, sleep, fatigue, sexual health, quality of life, and cognitive function will be recorded, along with sociodemographic information related to the study participants in a case report form (see Participant Booklet in "Supporting Documents" section of IRB). The research chart and Case Report Form (CRF) will be maintained in the research office of [name].

9.5 For HUD uses provide a description of the device, a summary of how you propose to use the device, including a description of any screening procedures, the HUD procedure, and any patient follow-up visits, tests or procedures. N/A

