The study team will meet and review all adverse events after five subjects have been randomized and received the SGB procedure or sham. Per NU IRB protocol, all UPIRSO's or PRNCs will be reported as soon as the PI becomes aware of it. As the PI is the injectionist, the likelihood of missing a UPIRSO is highly unlikely. If no SAEs/UPIRSO's are observed, the team will meet again after 10 subjects have been randomized. No UPIRSOs or SAEs have occurred in previous studies.

- ***What data are reviewed, including safety data, untoward events, and efficacy data?***

Participants who undergo the SGB with bupivacaine will experience a temporary sympathetic block of the right upper extremity and right face. Efficacy of the SGB will be confirmed by the presence of Horner's syndrome (miosis, abnormal contraction of the pupil; ptosis, drooping upper eyelid; and anhydrosis ,absence of facial sweat) and a temperature increase of the affected extremity, the latter the result of regional venodilation. The temperature of the right upper extremity will be monitored prior to and 30 minutes following the injection to confirm, along with a Horner's syndrome, successful SGB. These events are expected and confirm correct SGB placement. Events outside of those expected are what will be reviewed as stated above. The study team will be trained on the types of study related SAEs or AEs that should immediately be reported to the PI/IRB since they will not have access to the procedures records to maintain the blind.

- ***How the safety information will be collected***

Safety data will be collected with case report forms, at study visits, and by telephone calls with participant.

- ***The frequency of data collection, including when safety data collection starts.***

Title: SGB CA Study

Safety data is collected as soon as the participant agrees to participate and signs the informed consent document.

• ***Who will review the data?***

The PI will review the data with the study coordinator.

• ***The frequency or periodicity of review of cumulative data.***

Efficacy data will be reviewed at the conclusion of the study. Safety data will be reviewed after 5 are randomized, then after 10 are randomized. Thereafter, safety data will be reviewed every 6 months provided that no UPIRSOs are observed in those that have received the study procedure.

• ***The statistical tests for analyzing the safety data to determine whether harm is occurring.***

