13.0 Risks to Subjects*

13.1 List the reasonably foreseeable risks, discomforts, hazards, or inconveniences to the subjects related the subjects' participation in the research. Include as may be useful for the IRB's consideration, describe the probability, magnitude, duration, and

Title: SGB CA Study

reversibility of the risks. Consider physical, psychological, social, legal, and economic risks.

There are risks associated with participation in this study. Below is a description of the risks:

Stellate Ganglion Block with local anesthetic

Stellate ganglion injection carries the potential very rare risk of infection at the injection site, bleeding or blood clot formation at the injection site, seizures (sudden, uncontrolled muscle spasms and loss of consciousness) and nerve injury which may present as temporary paresthesia (numbness) and/or weakness. All of these rare risks are minimized with the use of fluoroscopic guidance (visualization with a type of x-ray). Other complications related to the stellate ganglion injection that can occur are puncture of the lung on the right during placement of the needle on the right neck, or an allergic reaction to the medications being injected into the subject. Temporary voice hoarseness, temporary mild shortness of breath, temporary difficulty swallowing, and temporary changes in your blood pressure may occur after the stellate ganglion injection from the numbing medicine. Possible reactions from the numbing medicine used in this study last 6-8 hours. Minor soreness at the injection site could last 1-2 days.

Tissue injection of saline (sham) below the surface of the skin

Needle placement carries the potential very rare risk of infection at the injection site, bleeding or blood clot formation at the injection site, temporary swelling of the right side of the neck from the injected liquid and an allergic reaction to the medications being injected into you. Minor soreness at the injection site could last 1-2 days.

Risk of Radiation from the x-ray

The cumulative radiation exposure from these tests is considered small and is not likely to adversely affect the subject or their disease.

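### No safety contact after discharge is dated before the 3-month visit, and the reviews after 5 and 10 women have no minimum follow-up

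*Combined protocol and SAP*

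**What the plan says.** All references are to the combined protocol and SAP.

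- **Observation after injection.** Section 9.3 has women "monitored in a reclining position for at least 20 minutes to assess potential adverse effects of the injection". Section 8.2 says "subjects will stay in the office for half an hour for observation", and section 9.2 (Visit 3) says "they will stay in the office for about half an hour for observation". The section on provisions to monitor the data adds: "The temperature of the right upper extremity will be monitored prior to and 30 minutes following the injection to confirm".
- **Next visit.** Section 9.2, Visit 4: "They will be asked to return to the clinical site 3 months following the injection procedure". The main study has five visits, and the injection is Visit 3.
- **Safety sources.** The monitoring section lists case report forms, study visits and telephone calls. It gives no dates or frequency for the calls.
- **Reviews.** "Safety data will be reviewed after 5 are randomized, then after 10 are randomized", and every 6 months after that. Section 8.2 and the monitoring section specify that the first five must have received the injection or sham.
- **Reassurance.** "As the PI is the injectionist, the likelihood of missing a UPIRSO is highly unlikely" (section 8.2, repeated in the monitoring section). Section 11.4 gives the injectionist no further contact with participants unless an adverse event needs his immediate attention.
- **Expected reactions.** Section 13.1 puts reactions to the anaesthetic at 6-8 hours and says, for both arms, "Minor soreness at the injection site could last 1-2 days". It also lists rarer complications of the injection, without onset times.
- **Contact started by the participant.** Section 23.2 says women will be told they can be seen about any concern between study visits.

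**The concern.** The reactions the protocol itself expects outlast the stay in the office, yet nobody is scheduled to ask about them until 3 months later. The early reviews exist to detect a problem while few women have been exposed. A review that finds no events is informative only if someone asked. Here the plan's stated protection is the injectionist's presence, and that gives direct observation on the procedure day only.

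Two things are at stake. One is the value of the 5- and 10-woman reviews as a check before more women are injected. The other is the completeness of adverse-event data generally, because short-lived reactions that were not reported at the time would have to be recalled at 3 months. The optional second injection, offered after the 3-month procedures, has the same gap: the next dated visit is Visit 5.

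**Working it through.** The plan states no figure on this point to reproduce, so the check has four parts.

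**1. Dated contacts around the injection (section 9.2)**

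- Before injection: the telephone call that checks hot-flash counts for eligibility, then Visit 2.
- Injection: Visit 3.
- After injection: Visit 4 at 3 months and Visit 5 at 6 months. Monthly diary-reminder calls follow in months 6-12, only for women who opt in.

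No visit or call is dated between Visit 3 and Visit 4. Section 11.1 mentions Months 1 to 6 and the 30 days before each visit, but section 9.2 schedules no monthly visits. The daily diary collects hot flashes and comments on them, not adverse events. Visit 4 repeats the Visit 2 procedures, and that list contains no adverse-event enquiry, although the monitoring section counts study visits as a source.

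**2. How many women have reached Visit 4 at each review**

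Inputs: N = 36 randomized (section 9.1), 30 (section 21.3) or 33 (15 + 18, section 21.2); accrual time T = 12 months (section 7.2). Assumption: even accrual at rate r = N/T per month.

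At the k-th injection, woman i has been followed for (k − i)/r months. She has reached Visit 4 if k − i ≥ 3r.

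| N | r | 3r | Review at k = 5 (largest k − i is 4) | Review at k = 10 (largest k − i is 9) |
|---|---|---|---|---|
| 36 | 3.0 | 9.0 | 0 of 5; longest follow-up 4/3 = 1.3 months | 1 of 10 (k − i = 9) |
| 33 | 2.75 | 8.25 | 0 of 5 | 1 of 10 (k − i = 9) |
| 30 | 2.5 | 7.5 | 0 of 5; longest follow-up 4/2.5 = 1.6 months | 2 of 10 (k − i = 8, 9) |

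Sensitivity to accrual time, for N from 30 to 36: if accrual takes 6-9 months, 0 of 5 and 0 of 10; if it takes 18-24 months, 0 to 1 of 5 and 4 to 6 of 10.

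The next review comes 6 months after the 10-woman review. By then a further 6 × 3 = 18 women (N = 36) or 6 × 2.5 = 15 women (N = 30) have been injected.

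**3. How many women are still inside the stated reaction windows**

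Spacing between injections is 12/36 = 0.33 months, about 10 days (12/30 = 0.4 months, about 12 days, for N = 30). At the 5th injection with N = 36, the earlier four women are about 10, 20, 30 and 40 days out. At the 10th, the other nine are at least 10 days out. So only the newest woman at each review is still inside the 6-8 hour or 1-2 day window. The others have passed through it without being asked.

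**4. What a clean review could show**

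With zero events in n women, the one-sided 95% upper bound on the event rate is 1 − 0.05^(1/n). This gives 45% for n = 5 and 26% for n = 10, with both arms pooled. These bounds assume every event was found, so without active enquiry even this limited assurance is not earned.

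**The case against.** The strongest reply is that safety reporting does not depend on visits. Collection runs from consent, staff are trained on which events to report at once, unanticipated problems go to the IRB on awareness, the injectionist can be called back for an adverse event, and women may ask to be seen at any time. This stands in part. A reader might infer that a review without events would reflect only a failure to ask, or that the reviews would hold almost no post-discharge data. The documents do not support either: spontaneous reports and undated calls are provided for, and the 3-month count depends on accrual speed. What the documents lack is a schedule for asking.

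Second, a reader might take the review triggers as the main fault. Part 3 of the working shows otherwise: at the planned pace, timing leaves one woman per review inside the windows, while missing enquiry affects all of them.

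Third, 20 minutes against half an hour can be read as a contradiction. It is not strictly one. Section 9.3 sets a floor, and a half-hour stay satisfies all three statements. The wording matters because a stay at that floor would end before the 30-minute temperature reading.

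Two further inferences go too far. Section 13.1 gives durations, not onset times, so it does not establish which complications would first appear after discharge. And no between-arm analysis of adverse events is described (no statistical safety test is planned), so a stated bias in adverse-event rates by arm cannot be claimed; incomplete ascertainment can.

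Finally, subject instructions and data collection forms are said to be in the IRB supporting documents, which are not part of the text reviewed. Call timing may be set there.

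**Conclusion.** The point holds as a gap in active safety enquiry. In the protocol text no post-discharge safety contact is dated before 3 months, the telephone calls named as a source have no timing, and the 5- and 10-woman reviews require no minimum follow-up. At planned accrual, 0 of 5 and about 1 to 2 of 10 women will have had a post-injection visit when those reviews are triggered. This rests on even accrual of 30 to 36 women over 12 months. Slower accrual would improve the second review but leave the first at 0 to 1 of 5. The observation wording is a lesser matter of reconciliation. The change should be made: it improves what the reviews can detect and uses a contact that the plan already names.

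**What to change.** 1. Give the safety telephone call in the monitoring section a stated time after every injection, including the optional second one, in both arms. Use the same fixed adverse-event questions for everyone. An existing team member who does not administer the outcome tests should make the call. The investigators should set the window in light of the durations in section 13.1.
2. Hold the 5- and 10-woman reviews once the 5th and 10th woman have completed that call.
3. Reconcile the observation wording in sections 8.2, 9.2 and 9.3 with the 30-minute temperature reading in the monitoring section. The duration is for the investigators to decide.

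**Cost.** About 36 short calls, or up to 36 × 2 = 72 if every woman has a second injection, plus protocol wording. There is also a small risk that symptom questions cue the caller or the woman herself to allocation, which matters because the primary outcome is a subjective diary. Neutral wording, identical in both arms, limits that risk without removing it.
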